**1. AMENDMENT HISTORY**

Amendment No.	Protocol Version No.	Date issued	Author(s) of changes	Details of Changes made
	0.1	15/10/2015	Dr [name]	Pre-sponsor approval version
	0.2	14/02/2017	Dr [name]	Revision of recruitment strategy, updated protocol details
	0.3	02/03/2017	Dr [name]	Sponsor changes made
	1	06/03/2017	Dr [name]	Sponsor approved version
	2	03/04/2017	Dr [name]	Revision following REC review
	3	01/06/2017	Dr [name]	Major amendment to recruitment strategy

**2. SYNOPSIS**

Study Title	Cerebral Haemodynamic Changes During Cognitive Testing: A Functional Transcranial Doppler (fTCD) study
Internal ref. no.	
Trial Design	Prospective, observational, case-control study
Trial Participants	Healthy Control Subjects, Patients with Mild Cognitive Impairment, Patients with Vascular Dementia and Patients with Alzheimer’s Dementia
Planned Sample Size	11 Healthy Control Patients, 11 Patients with Mild Cognitive Impairment, 11 Patients with Vascular Dementia and 11 Patients with Alzheimer’s Dementia
Follow-up duration	None
Planned Trial Period	7 Months
Primary Objective	To compare the beat-to beat cerebral blood flow velocity (CBFv) between patients with Mild Cognitive Impairment (MCI), patients with Vascular Dementia (VascD), patients with Alzheimer’s Dementia (AlzD) and age-, gender- and blood pressure (BP)-matched healthy control (HC) subjects during performance of the Addenbrooke’s Cognitive III (ACE-III) examination
Secondary Objectives	
 
1) To investigate whether performance of the Addenbrooke’s Cognitive III Examination is associated with differences in other beat-to-beat cerebral haemodynamic parameters, specifically autoregulation index (ARI), between MCI patients, VascD patients, AlzD patients, and age-, gender- and BP-matched HC subjects.
 
2) To assess the acceptability and feasibility of this protocol in patients with cognitive impairment in clinical practice.
 
3) To assess the reproducibility of measurements in cognitively impaired patient group at 3 months from initial measurement
 

Outcome Measure	
This is not an intervention study, and therefore it would not be appropriate to assess the classical primary and secondary outcome measures such as death and disability for this study. However, we intend to evaluate the following relevant outcomes:
 
 
1. The percentage of recruited subjects (HC, MCI patients, VascD patients and AlzD patients) able to comply with the full measurement protocol.
 
2. The percentage of measurements rejected because of aspects related to data quality during the analysis protocol, with recorded reasons.
 
3. Overall, the percentage of recruited subjects (healthy controls, MCI patients, VascD patients and AlzD patients) in whom values for the following parameters can be derived:
 

	

• % change of CBFv at baseline in response to performance of the ACE-III Cognitive Examination

• Autoregulation index (using the Tiecks model and from the phase, gain and coherence).

--	------------------------------------------------------------------------------------------------------------------------------------------------------------------------------------------------------------------------------------------------

### 3. ABBREVIATIONS

ACE-III	Addenbrooke's Cognitive Examination
AE	Adverse event
AlzD	Alzheimer's Dementia
AR	Adverse reaction
ARI	Autoregulation Index
BP	Arterial Blood Pressure
CA	Cerebral Autoregulation
CBF	Cerebral Blood Flow
CBFv	Cerebral Blood Flow Velocity
CI	Chief Investigator
CPP	Cerebral Perfusion Pressure
CrCP	Critical Closing Pressure
CRF	Case Report Form
CRO	Contract Research Organisation
CT	Clinical Trials
CVR	Cerebrovascular Resistance
CVRi	Cerebrovascular Resistance Index
dCA	Dynamic Cerebral Autoregulation
EC	Ethics Committee (see REC)
ECG	Electrocardiogram
EHI	Edinburgh Handedness Inventory
EtCO 2	End-Tidal Partial Pressure of Carbon Dioxide
FFT	Fast Fourier Transform
GCP	Good Clinical Practice
GP	General Practitioner
GPI	Gosling's Pulsatility Index
HC	Healthy Control
HR	Heart Rate
ICH	International Conference on Harmonisation of Technical Requirements for Registration of Pharmaceuticals for Human Use
ISF	Investigator Site File
LRI	Leicester Royal Infirmary
MCA	Middle Cerebral Artery
MCI	Mild Cognitive Impairment
NVC	Neurovascular Coupling
NHS	National Health Service
NICE	National Institute for Health and Care Excellence

NRES	National Research Ethics Service
PET	Positron Emission Tomography
PI	Principal Investigator
PIL/S	Participant/ Patient Information Leaflet/Sheet
RAP	Resistance Area Product
R&D	NHS Trust R&D Department
REC	Research Ethics Committee
SAE	Serious Adverse Event
SAR	Serious Adverse Reaction
SOP	Standard Operating Procedure
SUSAR	Suspected Unexpected Serious Adverse Reactions
TCD	Transcranial Doppler Ultrasound
TFA	Transfer Function Analysis
TMF	Trial Master File
UK	United Kingdom
VMR	Vasomotor Reactivity
VascD	Vascular Dementia

#### 4. BACKGROUND AND RATIONALE

Dementia is a syndrome which comprises an acquired decline in memory and other cognitive functions(s) in an alert (non-delirious) person that is sufficiently severe to affect daily life. It is the most common neurodegenerative disorder in the United Kingdom (UK); 850,000 people currently live with dementia in the UK, and that number is expected to rise to more than 1 million within the next 5 years [Alzheimer's Society 2014]. The annual cost to the UK of dementia is £23.6 billion [Alzheimer's Society 2014]. The most common type of dementia in the population (55%) is Alzheimer's dementia (AlzD), which is characterised pathologically by neuronal loss and the presence of amyloid plaques and tau neurofibrillary tangles. AlzD typically has an insidious onset and a slow progression. There are several diagnostic criteria, and commonly used criteria include; Diagnostic and Statistical Manual of Mental Disorders (DSM-IV) classification of neurocognitive disorders [American Psychiatric Association 2000], ICD-10 classification [World Health Organisation, 1992], and the National Institute on Aging-Alzheimer's Association (NIA/AA) criteria [McKhann, 2011]. The recently published DSM-V criteria have re-classified dementia as major and mild neurocognitive disorders [Simpson, 2014]. Vascular dementia (VascD) is the second commonest form of dementia (15%), and is suggested by the presence of vascular risk factors. The key pathological processes are subcortical white matter ischaemia and/or multiple cerebral infarcts. The onset is often abrupt, and the progression stepwise and irregular; cognitive deficits are often less uniform than those of Alzheimer's dementia. Vascular dementia is diagnosed according to NINDS-AIREN criteria [Roman et al 1993]. Mild cognitive impairment (MCI) affects up to 20% of older adults and describes a set of symptoms rather than a specific medical condition or disease. A person with MCI has subtle problems with one or more of the following: day-to-day memory, planning, language, attention and visuospatial skills [McDade et al 2015]. MCI clinically may comprise a group of heterogeneous conditions and may have differing aetiologies [Petersen 2004]. MCI can be diagnosed using the criteria set out by the International Working Group on Mild Cognitive Impairment [Winblad et al 2004]. Although MCI significantly increases the risk of developing dementia [Busse et al 2006], at present it is not possible to accurately predict which patients with MCI will progress to dementia.

In recent times, our knowledge regarding the pathogenic mechanisms of dementia has changed considerably. In contrast to previous thoughts about the pure neurodegenerative nature of AlzD, it is now well established that vascular dysfunction and haemodynamic disturbances play a role in AlzD, as well as in VascD [Sabayan et al 2012]; with several epidemiological studies reporting an association between vascular risk factors (e.g. hypertension, hyperlipidaemia, type 2 diabetes mellitus) and AlzD [Viswanathan et al 2009]. Furthermore, post-mortem examinations have shown that the brains of AlzD patients contain cerebrovascular pathologies [Cacabelos et al 2003, Gorelick

2004]. Research studies investigating the vascular contributions to cognitive decline have generally reported cerebral hypoperfusion [Keage et al 2012, Sabayan et al 2012], and it is thought that this hypoperfusion affects cellular health which in turn triggers neurodegenerative pathways [Ruitenberg et al 2005, Kalaria 2010].

Cerebral haemodynamics can be studied using techniques such as functional magnetic resonance imaging (fMRI), positron emission tomography (PET) or single-photon emission computed tomography (SPECT). However, these techniques are expensive, in the case of SPECT involve radiation, and there are feasibility issues which are particularly problematic for older populations, including the need to lie still for prolonged periods and to have no metal implants. Transcranial Doppler Ultrasonography (TCD) is a simple, non-invasive imaging modality with high temporal resolution which allows for continuous and bilateral recording of cerebral blood flow velocity (CBFv) through the major cerebral arteries [Aaslid et al, 1982]. Measurements can be taken at rest, or during brain activation tasks such as sensorimotor functions or cognitive tasks. TCD measurement performed during such brain activation tasks is commonly referred to as functional TCD (fTCD), and is the assessment of blood flow in response to a specific cognitive stimulus or mental operation, a concept known as neurovascular coupling (NVC). Although the exact mechanisms of NVC continue to be explored and evaluated, it is thought that cerebral activation triggers a haemodynamic response involving neurons, astrocytes, vascular cells and local metabolites [Carmignoto et al 2010, Girouard et al 2006]. Cerebral blood flow (CBF) is also strongly influenced by the arterial partial pressure of carbon dioxide (PaCO2) which also modulates the effectiveness of cerebral autoregulation (CA), defined as the ability of the brain to maintain a relatively constant CBF in response to significant changes in cerebral perfusion pressure (CPP). CA is improved by hypocapnia and impaired by hypercapnia [Aaslid et al 1989, Paulson et al 1990]. It has been shown that CA can be reliably assessed by evaluating CBF responses to changes in PaCO2, such as those induced by hypo- and hyperventilation respectively [Dineen et al, 2010]. This concept is known as assessing vasomotor (or CO2) reactivity (VMR).

In addition to studying CBFv, NVC and VMR, by using transfer function analysis (TFA) further haemodynamic data can be obtained and calculated using TCD and beat-to-beat blood pressure monitoring. These data include coherence, phase, gain, autoregulatory index (ARI), critical closing pressure (CrCP) and resistance area product (RAP). By examining the transfer of BP fluctuations to CBF as a measure of CA, TFA makes it possible to examine the effect of changes in arterial blood pressure (BP) on CBFv. It quantifies the extent to which the input signal, BP, is reflected in the output signal, CBFv, and was first proposed by Giller in 1990. The parameter which tests the

linearity between the input and output signals at each frequency is called the coherence, with values of coherence ranging between zero and one. Values of coherence approaching one indicate a perfect linear relationship between input and output (i.e. CBFv and BP). Although there is currently no consensus on the threshold at which good coherence is assumed, many studies have adopted a coherence of  $\geq 0.5$  to accept the relationship as significant [Panerai et al 1998, Panerai et al 2006]. Phase is equivalent to the shift in radians from 0 to  $2\pi$  (or degrees from  $0^\circ$  to  $360^\circ$ ) that would be required to align input (BP) with output (CBFV) at a given frequency, and so gives an indication of the relative timing of the two signals. The magnitude of the phase response may be an indicator of the integrity of the autoregulatory response; phase is positive in intact CA (CBFv recovers faster than changes in BP) and it tends to zero in impaired CA when CBFv tends to follow BP, during steady-state conditions [Panerai et al 1998, Birch et al 1995]. Gain is the ratio of the amplitude of the output signal to the input signal, and so indicates the magnitude of change in CBFv that is due to a change in BP. Although gain alone is not a reliable measure of CA, an increase in gain suggests that CA is impaired, whereas a low gain indicates an efficient CA [Giller 1990, Van Beek et al 2008].

The time domain approach in TFA is used to extract information about the CA mechanism from the analysis of mean BP, CBFv, heart rate (HR) and end-tidal partial pressure of carbon dioxide (EtCO2) with respect to time. In 1995 Tiecks et al derived a set of equations and curves based on the CBFv response to a sudden fall in induced by thigh cuff deflation. These equations and curves allow for the calculation of an autoregulatory index (ARI) from 0 to 9, where 0 represents absence of autoregulation i.e. CBF dependent on CPP, (a 'pressure-passive relationship') and 9 represents best measurable autoregulation. 'Normal' autoregulation is represented by an ARI of  $5 \pm 1$ . Other parameters obtainable in the time domain may also provide useful information regarding the integrity of dCA, including CrCP and RAP. CrCP is expressed in mmHg and is defined as the arterial pressure below which small vessels collapse and forward blood flow becomes zero, which in the cerebral circulation is equivalent to the sum of ICP and the contributions of vascular smooth muscle tone [Panerai 2003]. RAP is expressed in mmHg.s/cm and is an index of cerebrovascular resistance, which is equal to the total cerebrovascular resistance x cross-sectional area of the vessel [Evans et al 1988].

A meta-analysis of twelve TCD studies in AlzD and VascD [Sabayan et al 2012], reported significantly lower CBFv in patients with AlzD and VascD in comparison to healthy control subjects. CBFv was especially low in patients with VascD. In MCI, although there are limited data available, no significant differences in CBFv have been observed between MCI patients and healthy controls, unless restricting to amnesic MCI [Keage et al 2012].

Four studies which have used fTCD to investigate cerebral haemodynamic responses to brain activation in patients with dementia have reported conflicting findings; two found that individuals with AlzD had attenuated blood flow responses to cognitive demand, and two found no differences between dementia patients and controls. These studies used visual stimulation [Asil et al 2005, Gucuyener et al 2010, Rosengarten et al 2001], and a whispered verbal task, a thumb opposition task and a design discrimination task [Matteis et al 1998].

Cognitive testing with standardised assessment tools such as the Mini Mental State Examination, Montreal Cognitive Assessment and Addenbrooke's-III Cognitive Examination (ACE-III) is a key component of the formal diagnosis of dementia, yet the effects of these tests on cerebral blood flow and haemodynamics is unknown. The ACE-III [Hsieh et al 2013] is a widely used, validated, cognitive screening tool recommended for use by health practitioners and researchers in patients over 50 years old with suspected dementia. The ACE-III is available for free. The copyright is held by [name], ARC Federation Fellow and Professor of Cognitive Neurology at Neuroscience Research Australia, who is happy for the test to be used in clinical practice and research projects.

This protocol has been used successfully by this group to examine changes in CBFv in 40 healthy volunteers from the University of Leicester. The data from this analysis has been presented at an international conference and is currently undergoing peer review for publication. Therefore, this protocol has demonstrated feasibility in a healthy population and warrants further investigation for the utility in a patient population.

Therefore, the proposed study will investigate and compare the beat-to beat cerebral blood flow velocity (CBFv) between patients with Mild Cognitive Impairment (MCI), patients with Vascular Dementia (VascD), patients with Alzheimer's Dementia (AlzD) and age-, gender- and blood pressure (BP)-matched healthy control (HC) subjects during performance of the Addenbrooke's Cognitive III (ACE-III) examination. The proposed study will also investigate whether performance of the Addenbrooke's Cognitive III Examination is associated with differences in other beat-to-beat cerebral haemodynamic parameters, specifically autoregulation index (ARI), between MCI patients, VascD patients, AlzD patients, and age-, gender- and BP-matched HC subjects.

## **5. OBJECTIVES**

### **5.1 Primary Objective**

To compare the beat-to beat cerebral blood flow velocity (CBFv) between patients with Mild Cognitive Impairment (MCI), patients with Vascular Dementia (VascD), patients with Alzheimer's Dementia (AlzD) and age-, gender- and blood pressure (BP)-matched healthy control (HC) subjects during performance of the Addenbrooke's Cognitive III (ACE-III) examination

### **5.2 Secondary Objectives**

- 1) To investigate whether performance of the Addenbrooke's Cognitive III Examination is associated with differences in other beat-to-beat cerebral haemodynamic parameters, specifically autoregulation index (ARI), between MCI patients, VascD patients, AlzD patients, and age-, gender- and BP-matched HC subjects.
- 2) To assess the acceptability and feasibility of this protocol in patients with cognitive impairment in clinical practice.
- 3) To assess the reproducibility of measurements in cognitively impaired patient group at 3 months from initial measurement

## **6. STUDY DESIGN**

### **6.1 Summary of Trial Design**

This is a prospective, observational, case-control study.

Each participant will be required to attend the Cardiovascular Research Laboratory, [name], University Hospitals of Leicester NHS Trust, for one Transcranial Doppler Assessment lasting approximately 90 minutes.

### **6.2 Primary and Secondary Endpoints/Outcome Measures**

This is not an intervention study, and therefore it would not be appropriate to assess the classical primary and secondary outcome measures such as death and disability for this study. However, we intend to evaluate the following relevant outcomes:

- 1) The percentage of recruited subjects (HC, MCI patients, VascD patients and AlzD patients) able to comply with the full measurement protocol.
- 2) The percentage of measurements rejected because of aspects related to data quality during the analysis protocol, with recorded reasons.
- 3) Overall, the percentage of recruited subjects (healthy controls, MCI patients, VascD patients and AlzD patients) in whom values for the following parameters can be derived:
  - % change of CBFv at baseline in response to performance of the ACE-III Cognitive Examination
  - Autoregulation index (using the Tiecks model and from the phase, gain and coherence).

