## **7. ELIGIBILITY CRITERIA**

### **7.1 Overall Description of Trial Participants**

Patients with MCI, Patients with VascD and Patients with AlzD, together with age-, gender- and BP matched healthy volunteer control subjects (HC) will be recruited to enable the complete data analysis of 11 MCI Patients, 11 VascD Patients, 11 ALzD Patients and 11 HCs.

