### **8.7 Discontinuation/Withdrawal of Participants from Study Treatment**

Each participant has the right to withdraw from the study at any time and without giving a reason. A decision to withdraw at any time, or a decision not to take part, will not affect the standard of care that participant receives. In addition, the investigator may discontinue a participant from the study at any time if the investigator considers it necessary for any of the following reason:

- An inability to comply with study procedures
- Consent withdrawn
- Loss of capacity

In the case of withdrawal in the healthy control group, they will be replaced to ensure that there are 11 healthy control subjects with complete data analysis.

All of the above will be recorded in the case report form (CRF).

Prior to the study, we will ensure that the participant is aware that he/she is free to withdraw from the study at any time for any reason. However, should this situation occur we would like to keep all the health information and data that has been collected so far for the final analysis. This will be clearly stated in both the Participant (Patient and Volunteer) Information Leaflet and Participant (Patient and Volunteer) Consent Form.

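### Outcome 3, and possibly outcome 1, counts healthy controls together with patients, so it does not give the patient-only feasibility estimate that secondary objective 2 asks for

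*Combined protocol and SAP*

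**What the plan says.** Section 5.2 gives the second secondary objective as "To assess the acceptability and feasibility of this protocol in patients with cognitive impairment in clinical practice". Controls are not part of it.

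Section 6.2, with the same wording in the synopsis, lists three outcomes:

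- Outcome 1: "The percentage of recruited subjects (HC, MCI patients, VascD patients and AlzD patients) able to comply with the full measurement protocol".
- Outcome 2: "The percentage of measurements rejected because of aspects related to data quality during the analysis protocol, with recorded reasons".
- Outcome 3: "Overall, the percentage of recruited subjects (healthy controls, MCI patients, VascD patients and AlzD patients) in whom values" for the change in CBFv and for the autoregulation index can be derived.

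Section 7.1 plans for "complete data analysis of 11 MCI Patients, 11 VascD Patients, 11 ALzD Patients and 11 HCs". Section 4 reports earlier use of the protocol in 40 healthy volunteers and concludes that "this protocol has demonstrated feasibility in a healthy population and warrants further investigation for the utility in a patient population".

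Section 11 covers the comparison of haemodynamic parameters between groups. It gives no analysis, stratification, confidence interval or threshold for any of the three percentages.

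**The concern.** The objective and the outcome that should serve it refer to different populations. Outcome 3 is a single figure for everyone recruited, and on planned numbers a quarter of those people are controls. By the account in section 4, the open question is how the protocol performs in patients.

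Two things are at stake. First, the reported percentage would describe a mixture that depends on how many controls happen to be recruited, which is not a quantity objective 2 asks about. If controls succeed more often than patients, the mixture looks better than the patient result. Second, one percentage over four groups can look acceptable while one dementia group does badly, and that group may be the one of most interest for use in clinical practice.

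Because no reporting rule is written down, the choice between a pooled and a patient-only figure would be made after the results are known.

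**Working it through.** **The plan's own figure.** The documents state no expected feasibility rate, target or precision, so there is nothing to reproduce. The 11 per group comes from a statement about a 2-unit ARI difference, and this point does not depend on it.

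**Inputs from the documents.** There are 11 participants with complete data in each of four groups (section 7.1): 11 controls and 33 patients, 44 in all. The control share is 11/44 = 25%.

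**Inputs assumed.** Success rates in controls (pC) and patients (pP) are not given, so a range is shown. The three patient groups are given one common rate except in the last example.

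**Formula.** If controls make up a share w of those recruited, the pooled rate is w × pC + (1 − w) × pP. Its difference from the patient rate is w × (pC − pP).

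- *Equal numbers recruited:* w = 0.25, so the difference is 0.25 × (pC − pP).
- *Recruitment until 11 are complete in every group:* expected numbers recruited are 11/pC and 33/pP, so pooled = 44 / (11/pC + 33/pP). With pC = 100% and pP = 60%, this is 44 / (11 + 55) = 44/66 = 66.7%.

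With pC = 100%:

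| Patient rate | Pooled, equal numbers | Difference (points) | Pooled, recruit to 11 complete | Difference (points) |
|---|---|---|---|---|
| 80% | 85.0% | 5.0 | 84.2% | 4.2 |
| 70% | 77.5% | 7.5 | 75.7% | 5.7 |
| 60% | 70.0% | 10.0 | 66.7% | 6.7 |

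Other control rates, with equal numbers recruited:

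- Controls 90%, patients 80/70/60%: 2.5, 5.0 and 7.5 points.
- Equal rates: 0.
- Controls 80%, patients 90%: 0.25 × (80 − 90) = −2.5 points, so pooling understates.

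**Example in counts, exact (Clopper-Pearson) 95% intervals.** Suppose 11/11 controls and 24/33 patients succeed. The pooled figure is 35/44 = 79.5% (64.7 to 90.2). The patient figure is 24/33 = 72.7% (54.5 to 86.7), which is 6.8 points lower. If instead 8/11 controls succeed, the pooled figure is 32/44 = 72.7%, the same as in patients.

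**Hidden group.** The 24 patient successes could be MCI 10/11, AlzD 8/11 and VascD 6/11. The pooled figure is still 79.5%, while VascD is 6/11 = 54.5% (23.4 to 83.3).

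**The case against.** The other side has several good points.

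- *Pooling is not stated throughout.* Outcome 1 names the four groups in brackets and could be read as one percentage per group. Outcome 2 counts measurements and names no population. Even in outcome 3, the opening word might only sum up after outcomes 1 and 2. The first two points stand. On outcome 3 the plain reading is a single percentage over all four groups, and under either reading no per-group or patient-only figure is promised.
- *Upward bias is not established.* A reader might infer that the study's headline feasibility figure is inflated. The documents do not support that: none of the three percentages is ranked first or called a headline, and no success rate is given for controls or patients. The earlier 40 volunteers are described without age or success rate, whereas these controls are to be matched to patients on age, gender and blood pressure. The 5 to 37% rate of inadequate acoustic windows in section 8.2 is not split by group. Patients must also have capacity and be judged able to comply, which may narrow any gap. This stands, so overstatement is a possibility only.
- *Eleven per group is a number with complete data, not a number recruited.* This stands, and it is why the second set of columns is shown.
- *The denominator already reads as everyone consented.* Section 7.2 makes consent the point of enrolment, and the window check in section 8.2 follows it. That is a fair reading, but section 8.7 says "In the case of withdrawal in the healthy control group, they will be replaced", and nothing says whether replaced controls stay in the denominator. Dropping them would push the control rate towards 100%.
- *Nothing is lost, because group membership is known.* The patient figure can indeed be computed later. That does not make it the specified outcome.

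**Conclusion.** The point holds in a limited form. Outcome 3 as defined does not estimate what objective 2 asks, because it includes a group outside the objective; outcome 1 may share the problem. This is true whatever the success rates turn out to be.

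The size and direction of any distortion are unknown. It is the control share of those recruited, about a quarter, times the control-patient gap. The figures of 5 to 10 points (equal numbers recruited) and about 4 to 7 points (recruitment to 11 complete per group) rest on assumed success of 100% in controls and 60 to 80% in patients. Equal rates give zero, and better success in patients reverses the sign. It would go too far to say that feasibility is overstated, or that all three outcomes are pooled.

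Objective 2 is secondary and no decision rule depends on the percentages, so this should be corrected but does not threaten the primary comparison.

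**What to change.** In section 6.2 and the synopsis:

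1. Report outcomes 1 and 3 separately for HC, MCI, VascD and AlzD, and for all patients combined, each with an exact 95% confidence interval. Do the same for outcome 2 where measurements can be attributed to a group.
2. Name the all-patient figure as the estimate for objective 2, with controls as a reference only.
3. State that the denominator is every consented participant, including those with inadequate windows and controls who were later replaced.

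The cost is a change of wording; no further data are needed. The reported figure may be less favourable and its interval wider: in the example above, 54.5 to 86.7% for 33 patients against 64.7 to 90.2% for 44 participants. Per-group figures will be very imprecise (8/11 has an interval of 39.0 to 94.0%) and should be presented as descriptive.
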